In spite of the recognition of inflammation as a driver of depression in those with HIV the basic underlying pathophysiology must be elucidated. Prior research investigating plasma inflammatory biomarkers in HIV-infected persons reported an association of depression with pro-inflammatory cytokines, such as interleukin-6 (IL-6), and depression. Yet, factors modulating longitudinal changes in depression with therapy, e.g. group support psychotherapy in HIV patients is poorly understood. We will longitudinally evaluate changes in plasma biomarker changes in participants on ART with standard of care depression interventions before and after implementing group psychotherapy. In Ugandans with HIV, IL-6 in plasma is associated increased risk of depression highlighting the importance of IL-6 and innate inflammation.

Objective

Determine if depression, which persists after depression treatment at 26 weeks, is associated with increased innate inflammation in a prospective cohort of HIV-infected Ugandans receiving SSRIs in which group psychotherapy is initiated.

Hypothesis: Among HIV-infected Ugandans with depression (A): initiating ART and SSRI therapy, structured weekly group psychotherapy coupled with SSRIs will reduce depressive symptoms, measured by the PHQ-9 and Hamilton Depression Rating Scale: (B) Those with persisting depression at 26 weeks will have increased plasma IL-6 and cortisol levels, reflective of ongoing systemic stress response.

Prediction: Innate inflammation (e.g. IL-6) and systemic stress responses (e.g. cortisol) will be higher at 26 weeks in those with persistent depression compared with those with resolved depression.

Experimental Plan:

We will enroll a prospective cohort of HIV-infected subjects with depressive symptoms and a control without depressive symptoms.

- The first 100 subjects - standard of care therapy including SSRI therapy
- The second 100 subjects – standard of care including SSRI therapy + Group Support Psychotherapy
- The third 100 non-depressed subjects- standard of care HIV therapy

We will assess PHQ-9 at baseline (pre-ART) and again at 26 weeks. PHQ-9 instrument has been used and validated in several African countries including Uganda.¹⁻⁹ The cut-offs for the PHQ-9 tool are “not depressed”

(score ≤ 4), “mild depression” (score 5-9), “moderate and moderately severe depression” (score 10-19), or “severe depression” (score ≥ 20).

Enrollment Criteria

- Age ≥ 18 years old and < 65 years
- Depressive Symptoms with PHQ-9 score ≥ 5
- Not suicidal (PHQ-9 question 9 score ≥ 2)
- Not severely depression (PHQ-9 score ≥ 20)
- Not Pregnant or Breastfeeding
- Provision of written informed consent
- Not receiving ART at study entry
- Outpatient, not requiring hospitalization

Non-depressed control group will have PHQ-9 < 5 and not suicidal but otherwise identical.

Screening: We will screen participants newly presenting to clinic (<3 months). We will check PHQ-9 score to evaluate for eligibility and record the baseline CD4 count. We will also record baseline demographics including biological sex and age. We will record all screened in screening log. We will also ask all women the date of their last menstrual period, their last pregnancy, and do a pregnancy test on all women ages 18-50 if otherwise eligible.

Baseline Measurements: Those with PHQ-9 ≥ 5 and ≤ 19 will be invited to consent as well as a non-depressed (PHQ-9 < 5) control group otherwise meeting enrollment criteria. Those consenting will have PHQ-9 recorded as well as Hamilton Rating Depression Scale,¹⁰ which has not been previously validated in Uganda. We will compare depression prevalence between the two scales. Of enrolled participants (PHQ-9 score > 5), We will collect plasma and cryopreserve at -80C for biomarker quantification. We will record the medications the participants are prescribed including antidepressants and ART. I will administer a questionnaire about relevant social factors to depression including a validated social support scale as well as the Stress and Adversity Inventory (STRAIN).

Week 12 Measurements of those depressed: At 12 weeks we will assess for depression using PHQ-9. We will record the medications the participants are on including antidepressants and ART. This is primarily a safety check. Those not depressed will not be contacted.

26 Week Follow Up Including HIV Viral Loads: We will again assess for depression using PHQ-9. We will record medications the participants are taking and measure plasma cytokines/biomarkers. We will again administer the social factor questionnaire including a validated social support scale as well as the STRAIN stress inventory tool. HIV plasma viral load will be checked per National Ugandan HIV guidelines. We will collect these data via review of the electronic medical record.

Cytokine measurement will be performed at baseline and 26 weeks.

Statistical Analysis: Our analysis will focus on:

1) Effect of Group Support Psychotherapy: We will compare the proportion of baseline depression with the proportion of persistent depression at week 26. We will use the PHQ-9 as a continuous variable, with changes from baseline to week 26.

2) Effect of biomarkers on persistent vs. resolved depression: We will compare those with persistent depression (PHQ-9 > 4 at week 26) versus resolved depression (PHQ-9 < 5 at week 26). We will assess baseline demographic and HIV parameters as well as log2-transformed plasma cytokines from week 0, week 26, and the change in biomarker values from week 0 to week 26. We will use Benjamini-Hochberg adjustment for multiple comparisons for the biomarkers unrelated to our a priori hypothesis (i.e. IL-6 association with persisting depression). If the distribution between groups is unbalanced for an important factor (e.g. age, sex as biological variable, anti-depressant use, HIV viral load), we will adjust as needed for differentially distributed variables between the cohorts. We will consider sex as a biological variable in our analyses, considering differential effects in women vs. men.

3) Effect of biomarkers on depressed vs non-depressed control group: We will compare those never depressed (PHQ-9 <5) and those depressed at baseline and at 26 weeks. We will also group those never depressed with those with resolved depression (PHQ-9 <5 at week 26) and compare with those with persistent depression (PHQ-9 >4 at week 26). We will assess baseline demographic and HIV parameters as well as log2-transformed plasma cytokines from week 0, week 26, and the change in biomarker values from week 0 to week 26. We will use Benjamini-Hochberg adjustment for multiple comparisons for the biomarkers unrelated to our a priori hypothesis (i.e. IL-6 association with persisting depression). If the distribution between groups is unbalanced for an important factor (e.g. age, sex as biological variable, anti-depressant use, HIV viral load), we will adjust as needed for differentially distributed variables between the cohorts. We will consider sex as a biological variable in our analyses, considering differential effects in women vs. men.

4) Baseline Cytokine Analysis: As a secondary outcome, subjects will be categorized into baseline groups of mild depression versus moderate or above depression. We will compare baseline plasma biomarker levels by group via linear regression of log2 transformed data. Any demographic covariates associated with depression will be included in the regression model. We will also compare by 9 am cortisol levels. We will assess whether age or sex are associated with biomarker responses.

5) Virologic Outcomes: As a secondary outcome, proportions of those with 26-week virologic suppression will be compared by those with persisting depression vs. resolved using Fisher's Exact test.

6) Depression Scale Comparison: We will compare prevalence of depression using the PHQ-9 and the HDRS. We will compare the proportions of those depressed at baseline and 26 weeks using McNemar's test.

7) Social Factors and Stress Assessment: We will analyze social factors and the STRAIN stress and adversity tool scores by baseline depression and control groups as well as those with persistent depression at 26 weeks using linear regression.

LIST OF ABBREVIATIONS AND DEFINITIONS OF TERMS

AE	Adverse events
ART	Antiretroviral Therapy
CD4	CD4+ T helper Cells
CRF	Case report form
HRDS	Hamilton Rating Depression Scale
HIV	Human Immunodeficiency Virus
IDI	Infectious Diseases Institute
IL-6	Interleukin-6
IRB	Institutional Review Board
KCCA	Kampala Capital City Authority

MU-JHU	Makerere University – John's Hopkins University Core Laboratory
PHQ-9	Patient Health Questionnaire 9 Item Depression Screening Tool
PI	Primary Investigator
SAE	Serious Adverse Event
SSRI	Selective Serotonin Reuptake Inhibitor
STRAIN	Stress and Adversity Inventory

TABLE OF CONTENTS

LIST OF ABBREVIATIONS AND DEFINITIONS OF TERMS	6
1. INTRODUCTION	10
1.1. Disease Setting/Patient Population	10
1.2. Background and Rationale.....	10
2. STUDY OBJECTIVES AND ENDPOINTS.....	12
2.1. Objectives	12
2.2. Study Hypothesis	12
3. SUBJECT SELECTION	13
3.1. Inclusion Criteria	13
3.2. Exclusion Criteria.....	14
4. TREATMENTS OF SUBJECTS.....	14
4.1. Allocation to Treatment/Group	14
4.2. Drug Supplies.....	14
5. STUDY PROCEDURES	14
5.1. Screening.....	14
5.2. Study Period.....	15
5.3. Subject Withdrawal.....	15
6. ASSESSMENTS	15
6.1. Safety	15
6.2. Pregnancy Testing	16
6.2.1. Sample Handling.....	16
7. ADVERSE EVENT REPORTING	16
7.1. Adverse Events.....	16
7.2. Serious Adverse Events	16
7.3. Severity Assessment	17

1. INTRODUCTION

Depression in HIV is a complex co-morbidity with both social factors such as stigma¹¹ as well as biologic components.¹² Disruptions in neurotransmitters such as serotonin and catecholamines are known to cause depression.¹³ Inflammation caused by diseases such as stroke, diabetes, and HIV is associated with higher rates of depression.¹⁴ HIV causes inflammation throughout the body, but since the virus can cross the blood-brain-barrier, HIV can replicate in and target the brain causing neuroinflammation which predisposes depression.¹⁵ However the pathophysiology of the role of inflammation in comorbid depression and HIV is poorly understood.

1.1. Disease Setting/Patient Population

Participants will be selected from the HIV patients in the IDI or KCCA clinics. We will select ART naïve, adults who are newly enrolled in clinic (<3 months). We will screen them for depression. Those with depression will be followed for 26 weeks and have their charts checked for viral load data at 26 weeks.

1.2. Background and Rationale

Depression in HIV is common and causes poor HIV outcomes. Depression prevalence in HIV-infected persons ranges from 13 to 78% as compared to 5% in the general population.^{16, 17} Adherence to antiretroviral medication and subsequently viral suppression is a life-saving treatment in HIV.¹⁸ However, depression has been shown to reduce engagement in care as well as adherence to medication.¹⁹ There is also evidence that depression is associated with poorer levels of viral suppression and even mortality.^{20, 21}

Depression in HIV has negative public health implications. Depression decreases the likelihood that people will engage in HIV care, adhere to treatment, and respond to HIV therapy. Those with depression and HIV are less likely to return to health and remain more likely to transmit the virus.^{22, 23} Because of this, treatment of HIV is an important key to prevention; lower rates of engagement in and adherence to HIV treatment due to depression means others remain at risk.^{24, 25}

Growing evidence shows depression has an inflammatory component. Depression has higher prevalence in neuroinflammatory disorders including stroke, diabetes, and HIV.¹⁴ These conditions alter the blood brain barrier allowing for infiltration of immune cells and increased cytokine signaling. While many diseases make people chronically ill such as hepatitis B, only some have increased prevalence of depression such as HIV. This observation does not suggest that the psychosocial impacts of chronic life-threatening illness do not contribute to depression but does imply that neuroinflammatory effects in diseases such as HIV can be additive or synergistic in the pathogenesis of depression.

Depression in HIV, even when participants have virologic suppression, is often resistant to standard psychiatric treatment, and treatment for depression among people living with HIV is understudied. While there are many treatment modalities for depression, a significant proportion of patients do not respond to treatment.²⁶ Also, while there are a few studies looking at treatment of depression specific in HIV, the data are scant.^{27, 28} More work on depression treatment in those with HIV is needed, particularly in low-income countries in sub-Saharan Africa given the high prevalence of HIV.

Psychotherapy, long known to improve depression, is increasingly being shown to decrease inflammation suggesting the underlying mechanism. Psychotherapy is a mainstay of depression treatment and has been shown to decrease IL-6 and TNF-a two pro-inflammatory cytokines linked with depression,²⁹ as well as IL-6, and CRP in women post coronary artery bypass.³⁰ Psychotherapy may work through a neuroendocrine mechanism with decreased psychological symptoms correlating with decreased stress biomarkers such as cortisol. Antoni et al. found cognitive-behavioral stress management interventions decreased both cortisol and depressive symptoms over controls in U.S. men who have sex with men (MSM) and are living with HIV.³¹ However, given the differences in cultures, psychological, and social factors between American MSM and sub-Saharan African heterosexual individuals, adjustments to similar interventions are needed.

Psychotherapy: Evidence in sub-Saharan Africa. We recently published a depression intervention review for Africans with HIV.³² We found multiple interventions feasible and acceptable in their community. Specifically Nakimuli-Mpungu in Uganda has found that group support psychotherapy is a culturally sensitive intervention, which enhances social support, teaching coping skills, and income-generating skills thereby treating depression.³³⁻³⁶ Given the success in sub-Saharan Africa and that group psychotherapy is scalable, as it can be taught to lay health workers, this presents an opportunity to treat depression even in poor and rural areas.

This work could be helpful not only for people with HIV but also potentially for patients with other inflammatory diseases such as lupus where there is also a higher prevalence of depression.³⁷ The past work in immunologic differences in those with and without depression in HIV suggests an opening to further investigation.

Resolution of Depression for Some with ART: Our previous work in Uganda has shown that while a portion of HIV-infected people remain depressed even after starting ART, a large percentage resolve with ART alone. In our previous studies in cryptococcal disease, 65% (N=217) of 325 cryptococcal survivors were depressed via the CES-D scale at time of ART initiation and of those depressed, at 8 weeks 47.5% (N= 103) were no longer depressed, 31% (N=67) remained depressed, and 21.7% (N=47) had died or were lost to follow up (unpublished data). Similarly, 59% in those with cryptococcal antigenemia (N=207) were depressed pre-ART compared to 30% in 125 HIV-infected controls pre-ART with a mean CD4 count of 242 ± 119 cells/ μ L.³⁸ In those with meningitis, we followed depression via CESD and found a significant portion of the depression resolved with HIV therapy but no depression specific therapy. Similarly our co-mentor [name] recently presented a poster at CROI from a subset of participants in the Rakai cohort with available follow up data.³⁹ The researchers found among 333 people with HIV and ART naïve, 22% (N=73) were depressed via CESD score at baseline and 8.4% (N=28) 2 years later. Thus, in this cohort 38% (28/73) had persistent depression at 2 years with HIV therapy alone. [name] co-authored another study looking at ART naïve, HIV-infected Ugandans and found that the rate of persistent depression was 25% over 1 year.⁴⁰

2. STUDY OBJECTIVES AND ENDPOINTS

2.1. Objectives

- 1) Among depressed HIV-infected Ugandans, determine if the resolution of depression at 26 weeks of HIV therapy is improved with group psychotherapy.
- 2) In the same population determine if persistent depression is associated with higher levels of innate inflammation. Also, compare baseline and follow up inflammation among depressed compared to non-depressed control group.
- 3) Evaluate if viral suppression levels at 26 weeks are improved by group psychotherapy.

Endpoints

- 1) Depression score via patient health questionnaire (PHQ-9) at screening (total screened and total enrolled) and at 26 weeks (total enrolled) comparing those in the observational cohort and those in the intervention cohort.
- 2) Biomarkers associated with depression including IL-6 measured from plasma as well as morning cortisol levels at screening and 26 weeks.

2.2. Study Hypothesis

Hypothesis: Among HIV-infected Ugandans with depression (A): initiating ART and SSRI therapy, structured weekly group psychotherapy coupled with SSRIs will reduce depressive symptoms, measured by the PHQ-9 and Hamilton Depression Rating Scale: (B) Those with persisting depression at 26 weeks will have increased plasma IL-6 and cortisol levels, reflective of ongoing systemic stress response.

Prediction: Innate inflammation (e.g. IL-6) and systemic stress responses (e.g. cortisol) will be higher at 26 weeks in those with persistent depression compared with those with resolved depression.

STUDY DESIGN

We will enroll a prospective cohort of HIV-infected subjects with depressive symptoms as well as a non-depressed control group.

In the depressed groups we will assess PHQ-9 at baseline (pre-ART), 12 weeks and 26 weeks. (**Figure 1**). PHQ-9 instrument has been used and validated in several African countries including Uganda.¹⁻⁹ The cut-offs for the PHQ-9 tool are “not depressed” (score ≤ 4), “mild depression” (score 5-9), “moderate and moderately severe depression” (score 10-19), or “severe depression” (score ≥ 20). We will also use the Hamilton Rating Depression Scale (HRDS),¹⁰ which has not been previously validated in Uganda. We will compare depression prevalence between the two scales. We will also have a second non-depressed control group who will be followed similarly to the observational group but without SSRIs or the 12 week safety check.

[figure not shown]
3. SUBJECT SELECTION

The following eligibility criteria are designed to select subjects for whom protocol treatment is considered appropriate.

Participating sites:

- 1) Infectious Disease Institute (IDI)/ Mulago Hill Complex, Kampala, Uganda
- 2) Kampala Capital City Authority (KCCA) Clinics Kampala, Uganda
 - Kawaala
 - Kawempe
 - Kisenyi
 - Kiswa
 - Kitebi
 - Komamboga

Figure 1. Enrollment Plan

SOC includes: tenofovir/lamivudine/dolutegravir; Referral and transport to local psychiatry for SSRI therapy and follow up

3.2. Exclusion Criteria

Subjects presenting with any of the following will not be included in the study:

1. Those not meeting enrollment criteria.

4. TREATMENTS OF SUBJECTS

4.1. Allocation to Treatment/Group

The first half of the depressed participants (100 subjects) will be in the observational cohort.

The second half of the depressed participants (100 subjects) will be in the intervention cohort and receive group psychotherapy.

A second non-depressed control group (100 subjects) will be added for another observational cohort.

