8. DATA ANALYSIS/STATISTICAL METHODS

8.1. Sample Size Determination

Depression Intervention:

We will power for a reduction in IL-6 between those with persistent and resolved depression at 26 weeks. Based on our systematic review, the reduction in depression score for psychotherapy is 73% from baseline.³² However response rates vary. Another review found the score reduction was 20% when compared to controls.⁴² We then calculated a range of possible sample sizes seen in **Statistics Plan**.

Assuming that 25% of the psychotherapy group will have persistent depression at week 26 (with equal sample sizes, 80% power, and two-sided alpha = 0.05) and I want a delta of .5, we need a total sample size of 168

participants. The prior study had a 22% non-completion rate for group therapy.³⁴ To account for non-completion and up to a 5% loss to follow-up, I estimate a sample size of 200 participants.

Subject Recruitment/Number needed to screen

[figure not shown]
I postulate that the baseline depression rate in these ART naïve subjects would be about 25%.⁴³ Thus we would need to screen 800-1000 HIV+ people.

The non-depressed control group will come out of those screened and not add to the total number screened.

These will be enrolled from the Infectious Disease Institute or three clinics that refer to it. As noted in the preliminary data section, we are currently working on a study in those found clinics and have found we can get about 15 new patients with CD4 <100 cells/uL a month (unpublished data). Our experience is that there are many more presenting with higher CD4 cells/uL counts, or about 150 new individuals a month. Taken these patient sources we estimate we could screen 800-1000 participants over 2.2 years from our 4 clinics and given not all participants will agree to participate we estimate that we can enroll the group over 2.5 years.

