8.2. Analysis of Endpoints

- 1) *Effect of Group Support Psychotherapy:* We will compare the proportion of baseline depression with the proportion of persistent depression at week 26. We will use the PHQ-9 as a continuous variable, with changes from baseline to week 26.
- 2) *Effect of biomarkers on persistent vs. resolved depression:* We will compare those with persistent depression (PHQ-9 ≥ 5 at week 26) versus resolved depression (PHQ-9 < 4 at week 26). We will assess baseline demographic and HIV parameters as well as log₂-transformed plasma cytokines from week 0, week 26, and the change in biomarker values from week 0 to week 26. We will use Benjamini-Hochberg adjustment for multiple comparisons for the biomarkers unrelated to our *a priori* hypothesis (i.e. IL-6 association with persisting depression). If the distribution between groups is unbalanced for an important factor (e.g. age, sex as biological variable, anti-depressant use, HIV viral load), we will adjust as needed for differentially distributed variables between the cohorts. We will consider sex as a biological variable in our analyses, considering differential effects in women vs. men.
- 3) *Effect of biomarkers on depressed vs non-depressed control group:* We will compare those never depressed (PHQ-9 < 5) and those depressed at baseline and at 26 weeks. We will also group those never depressed with those with resolved depression (PHQ-9 < 5 at week 26) and compare with those with persistent depression (PHQ-9 > 4 at week 26). We will assess baseline demographic and HIV parameters as well as log₂-transformed plasma cytokines from week 0, week 26, and the change in biomarker values from week 0 to week 26. We will use Benjamini-Hochberg adjustment for multiple comparisons for the biomarkers unrelated to our *a priori* hypothesis (i.e. IL-6 association with persisting depression). If the distribution between groups is unbalanced for an important factor (e.g. age, sex as biological variable, anti-depressant use, HIV viral load), we will adjust as needed for differentially distributed variables between the cohorts. We will consider sex as a biological variable in our analyses, considering differential effects in women vs. men.

*Depression Defined as PHQ-9 score 5-19 (severely depressed excluded)

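### Allocation by enrolment order ties cohort to enrolment period, so Objectives 1 and 3 and Endpoint 1 can show a before/after association but not an improvement caused by group psychotherapy

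*Combined protocol and SAP*

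**What the plan says.** Section 4.1 fixes the order: "The first half of the depressed participants (100 subjects) will be in the observational cohort", then "The second half of the depressed participants (100 subjects) will be in the intervention cohort and receive group psychotherapy". The Experimental Plan in the synopsis gives the same sequence, and the synopsis describes the study as measuring change "before and after implementing group psychotherapy". Section 8.1 gives the duration: "we estimate that we can enroll the group over 2.5 years".

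Objective 1 in section 2.1 is to "determine if the resolution of depression at 26 weeks of HIV therapy is improved with group psychotherapy". Objective 3 asks the same kind of question about viral suppression. Endpoint 1 is the depression score, "comparing those in the observational cohort and those in the intervention cohort".

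Section 8.2 item 1, whose heading names the effect of the therapy, reads: "We will compare the proportion of baseline depression with the proportion of persistent depression at week 26". It adds PHQ-9 change as a continuous variable, but names no between-cohort test and no covariates. The clause on adjusting for unbalanced factors stands under items 2 and 3, the biomarker analyses. Enrolment date is not among its examples.

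On the non-depressed controls, the Experimental Plan lists them last ("The third 100 non-depressed subjects- standard of care HIV therapy"), section 4.1 says they will be added, and section 8.1 says they come from those screened. None of these says when they are enrolled.

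**The concern.** Everyone in the observational cohort is enrolled before anyone in the psychotherapy cohort. Anything else that changes between the two periods is carried into the comparison: clinic mix, access to SSRI treatment through the outside psychiatry referral, ART practice, staff, or raters' experience with the Hamilton scale.

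The background is also large. Section 1.2 reports that much depression in this setting resolves once ART starts, with no depression treatment. A shift in that background rate could create an apparent therapy effect or hide a real one. At stake is the wording of the conclusion on Objectives 1 and 3. The biomarker comparison of non-depressed with depressed participants has a smaller version of the same problem if the controls are recruited in one block.

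**Working it through.** **The plan's own figure.** Section 8.1 gives 168 participants. That reproduces as 42 + 126 (a 1:3 split, difference 0.5 read as SD units, two-sided 0.05, 80% power). It is the size for IL-6 in persistent versus resolved depression. The plan has no sample size for psychotherapy versus observation, so there is no figure to reproduce for this contrast.

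**1. Distance in time.** Assume uniform enrolment over 2.5 years = 30 months. Each cohort takes 30/2 = 15 months, and the cohort midpoints are 15 months apart.

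**2. What adjustment can do.** Scale enrolment time t from 0 to 1, with cohort = 1 when t ≥ 0.5.
- *Period indicator (first or second half).* It is identical to cohort. A model with intercept, cohort and period has rank 2 of 3, so the two are completely aliased.
- *Linear time.* Covariance = 0.375 − 0.5 × 0.5 = 0.125; var(t) = 1/12; var(cohort) = 1/4. Correlation = 0.125/√(1/48) = 0.866. Variance inflation = 1/(1 − 0.75) = 4.0. The term is estimable but costly. For a 0.5 SD effect with 100 per cohort, the standard error rises from √(2/100) = 0.141 to √(4 × 2/100) = 0.283 SD, and power falls from Φ(3.54 − 1.96) = 94% to about Φ(1.77 − 1.96) = 42%.
- *Shape of the drift.* Simulation with 4,000 runs, no therapy effect, and an assumed drift of 0.3 SD between cohort means:

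| Drift | Unadjusted estimate; p<0.05 | With linear time: estimate; p<0.05 |
|---|---|---|
| Linear | −0.30 SD; 56% | −0.01 SD; 5% |
| Step at the switch | −0.30 SD; 57% | −0.30 SD; 18% |

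Linear time removes linear drift. After a step at the switch the whole bias remains; rejections fall only because the standard error has grown.

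**3. Illustrative size on persistence.** Inputs: 100 per cohort less the plan's 5% loss = 95; two-sided 0.05; 25% persistent in the second cohort (the section 8.1 assumption), with no part of the difference due to therapy. The first-cohort rates are assumptions.

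Rejection probability = Φ((d − 1.96·SE0)/SE1) + Φ((−d − 1.96·SE0)/SE1), where SE0 = √(2·p̄(1 − p̄)/95) and SE1 = √((p1(1 − p1) + p2(1 − p2))/95).

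| First → second cohort | d | SE0 | SE1 | p<0.05 |
|---|---|---|---|---|
| 28% → 25% | 0.03 | 0.0640 | 0.0640 | 7.5% |
| 30% → 25% | 0.05 | 0.0648 | 0.0647 | 12% |
| 35% → 25% | 0.10 | 0.0665 | 0.0661 | 32% |
| 38% → 25% | 0.13 | 0.0674 | 0.0667 | 49% |

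**4. Section 8.2 item 1 as written.** Depressed participants enter with a PHQ-9 of at least 5, so the baseline proportion depressed is 100% by construction, and any resolution counts as improvement. In the first cohort cited in section 1.2, 103/217 = 47.5% of depressed cryptococcal survivors were no longer depressed at 8 weeks. A cohort followed for 2 years on HIV therapy alone had 38% persistent depression, so 62% resolved. A baseline-to-week-26 change cannot tell such resolution from an effect of psychotherapy.

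**The case against.** The before/after design is deliberate and stated, and the documents claim no randomisation. The sample size rests on IL-6 in persistent versus resolved depression, which is not a cohort contrast. Clinic, CD4 count, baseline PHQ-9, age and antidepressant use are all recorded, so some of the likely drift can be measured. Section 8.2 item 1 contains no between-cohort difference that could be misattributed.

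Most of this stands and limits the point:
- A reader might infer that no covariate adjustment can help because cohort and calendar time are fully collinear. That is too strong. Only the half-period indicator is fully aliased; recorded factors can be adjusted for, and linear time is estimable.
- A reader might take the 25% and 38% in section 1.2 as the drift to expect. They come from different studies, over 1 year and 2 years, and neither shows change over time in these clinics.
- A reader might infer that the controls are enrolled after both depressed cohorts. Third may be only list order; the documents leave the timing open.

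What does not stand is that a deliberate design licenses the wording of Objectives 1 and 3. The absence of a contrast from item 1 is a further gap, because Endpoint 1 calls for one.

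**Conclusion.** The point holds as a limit on what the trial can conclude, not as an internal contradiction. Objectives 1 and 3 and Endpoint 1 depend on a non-concurrent contrast. Unmeasured or abrupt changes at the switch cannot be separated from a psychotherapy effect without assuming the form of the drift. Section 8.2 item 1 does not specify that contrast, and what it does specify mixes the therapy with resolution on ART alone.

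The size is conditional. Under the assumed drifts, the chance of a spurious difference at the 5% level runs from about 7.5% (3 points of drift) to 49% (13 points). A small drift does modest harm; the large figures need 10 to 13 points, and nothing in the documents shows that such drift will occur. The results also assume 95 evaluable per cohort and, for the time model, uniform enrolment. Drift in the other direction could hide a benefit. The persistent-versus-resolved IL-6 comparison is affected less directly, and this point does not invalidate it.

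**What to change.** 1. **Sections 2.1 and 8.2 item 1.** Reword Objectives 1 and 3, Endpoint 1 and item 1 to say that the observational-versus-intervention contrast is a non-concurrent, before/after association that does not by itself establish an effect of psychotherapy. Make the same change in the synopsis.
2. **Section 8.2 item 1.** State the between-cohort comparison of week-26 PHQ-9 and of persistent depression, adjusted for baseline PHQ-9, clinic, CD4 count, age and sex. Add a sensitivity analysis with enrolment date, and say that it relies on the assumed form of the drift and has about four times the variance if the term is linear.
3. **Section 4.1.** Enrol the 100 non-depressed controls prospectively and evenly across the whole enrolment period from those screened, that is, about 50 alongside each depressed cohort. They cannot be picked from the screening log afterwards, because they must be off ART at entry and give baseline plasma.

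The cost is a more modest claim about psychotherapy, slightly more analysis, and a recruitment schedule for the controls. No participants are added.

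Randomising enrolment blocks would give concurrent cohorts and is open to the sponsor, but it is a trade-off and not part of the required change. It brings clustering by block, allocation that recruiters can foresee, possible contamination, and the need to have therapy ready from the start.
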